5.4.5 Handling of Missing Data

Study variables could be missing for patients who withdrawn from the trial or for specific visits. We will report reasons for withdrawal.

Patient with missing in response outcomes will be considered as no responders. Patients without any post-baseline assessment will be considered as non-responders or without clinical benefit.

The analysis of timed endpoints is based on a Kaplan-Meier method, therefore, not affected by patient withdrawals (as they are censored) provided that dropping out is unrelated to prognosis.

For the analysis of maximum tumor shrinkage only observed cases will be used.

The other variables will be managed with simple imputations methods (last observation carried forward). The effect that any missing data might have on results will be assessed via sensitivity analysis.

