6.6 Translational Research

The molecular study involves the collection, processing, temporary storage, and shipment of samples from consenting patients enrolled in centers selected for participation in the study. The study plan includes collection and initial processing of tumor tissues and blood samples to a central laboratory that will be used to identify dynamic biomarkers that may be of prognostic value or predictive of response/resistance to INCMGA00012 (retifanlimab) treatment.

The exploratory analysis will be performed only if an adequate number of samples is available at the EoS. Since the identification of new markers that correlate with disease activity and the efficacy or safety of treatment is rapidly developing, the definitive list of analyses remains to be determined, but may include determination of markers such as but not limited to PD1, PD-L1, HIV, and HPV status.

Tumor-based biomarkers may include description of immune cells, gene expression profiling including tumor mutation burden, and/or measurement of protein levels for immune-related and tumor-related proteins.

Blood-based biomarkers may include serum cytokines, circulating immune cells, and circulating tumor cells.

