8.6 Missing Data Management

Study variables could be missing for patients who withdrawn from the trial or for specific visits. We will report reasons for withdrawal. Patient with missing in response outcomes (ORR and CBR) will be considered as no responders. Other outcomes will be managed with simple imputations methods. The effect that any missing data might have on results will be assessed via sensitivity analysis of study sets.

For PFS and DoR, patients without a date of disease progression or death will be analyzed as censored observations on the date of last tumor assessment. If no post-baseline tumor assessment is available, patients will be censored at the date of randomization + 1 day. Data for patients with an event who missed two or more scheduled assessments immediately prior to the event will be censored at the last tumor assessment prior to the missed visits.

For OS, patients who are not reported as having died will be analyzed as censored observations on the date they were last known to be alive. If no post-baseline data are available, OS will be censored at the date of randomization + 1 day.

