2.3 Exploratory Objectives

- To determine the efficacy –as determined by the ORR, CBR, and 6-month PFS based on immune-related RECIST (irRECIST).
- To evaluate predictive or prognostic, tumor- and/or immune-related biomarkers associated with disease activity status or response to treatment.
- To identify possible mechanisms of resistance to study treatments through the comparative analysis of potential biomarkers from paired pre-treatment and post-progression tumor and/or blood samples.
- To assess impact of INCMGA00012 on HIV control in participants who are known to be HIV-positive.

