3.4 Exploratory Endpoints

- ORR, CBR, and 6-month PFS as per irRECIST.
- Relationship between tumor- and/or immune-related biomarkers, and efficacy in tumor tissue and/or liquid biopsy.

- Changes from baseline in the CD4-positive cell count and HIV viral load in participants who are known to be HIV-positive.

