4 ANALYSIS SETS

The following sets will be analyzed:

- **Screening:** Patients who were present at the screening visit.
- **Safety and FAS (Full Analysis Set) Set:** patients who receive at least one dose of study medication.

Efficacy and Safety endpoints will be analyzed on the Safety/FAS set.

FAS set will be considered the primary population for the analysis.

- **Per-protocol (PP) set:** All patients that accomplish selection criteria, receive at least one drug exposure, and receive the protocol required study drug exposure and processing. Criteria for determining the “per protocol” (PP) group assignment would be established by the Steering Committee before the statistical analysis begins. This analysis will only occur if this set differs by $\geq 10\%$ from the FAS set.

The primary and secondary efficacy analyses will be performed on the FAS and PP sets.

- **Exploratory Set:** All patients with biomarker evaluable samples with the assay and alternative platforms that accomplish selection criteria and receive at least one drug exposure.

Exploratory analysis will be performed on exploratory set. A separate analysis report for such assessments will be written.

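### The residual carry-forward rule in SAP 5.4.5 does not exempt follow-up biomarkers, CD4 count or HIV viral load; followed as written, it can turn missing samples into no change (minor)

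*SAP*

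**What the plan says.** SAP 5.4.5 treats missing response as non-response, censors time-to-event endpoints, and uses observed cases only for maximum tumor shrinkage. Everything else falls under one sentence: "The other variables will be managed with simple imputations methods (last observation carried forward". It then promises that "The effect that any missing data might have on results will be assessed via sensitivity analysis", without naming a method. Protocol 8.6 is less specific ("Other outcomes will be managed with simple imputations methods") and does not mention carrying values forward.

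Three exploratory aims rest on samples taken after baseline:

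- The resistance objective in SAP 2.3 is a "comparative analysis of potential biomarkers from paired pre-treatment and post-progression tumor and/or blood samples".
- Protocol 6.6 intends to "identify dynamic biomarkers that may be of prognostic value or predictive of response/resistance".
- SAP 3.4 lists "Changes from baseline in the CD4-positive cell count and HIV viral load in participants who are known to be HIV-positive".

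The Exploratory Set in SAP 4 is "All patients with biomarker evaluable samples with the assay and alternative platforms that accomplish selection criteria and receive at least one drug exposure", and of the exploratory work the SAP says that "A separate analysis report for such assessments will be written". SAP 5.4.7 relates markers to ORR, CBR, PFS and irPFS but gives no rule for missing samples.

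**The concern.** Biomarkers, CD4 count and viral load are not among the variables with their own rule, so the residual sentence is the only written rule that reaches them. For a change-from-baseline measure, carrying the baseline value forward records a change of exactly zero that nobody observed.

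The gaps are unlikely to be random. Without delays C3D1 falls on day 57, and a patient who stops or dies earlier has no C3D1 sample. Those patients also have short PFS and usually no response, so a filled-in zero can become a label for poor outcome. Tissue at progression is optional, so missing pairs are expected there. HIV-positive patients must enter with an undetectable viral load (exclusion criterion 18), so a carried-forward baseline reads as maintained control.

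At stake are the size of marker changes, some marker-outcome associations, and the account of HIV control. The primary result is not.

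**Working it through.** **What the rule puts in each gap**

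- C3D1 blood missing: baseline, the only earlier scheduled value, so change is zero.
- Progression tissue missing: baseline tissue, so the pair shows zero change.
- Progression blood missing: the C3D1 value if there is one, otherwise baseline. Change is zero only in the second case.
- Viral load missing: the last observed value, which is undetectable unless a rebound was already recorded.
- Baseline-only markers (for example PD-L1 or HPV status at entry): nothing earlier exists to carry, so no effect.

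**Inputs.** N = 18 is from SAP 1.6 (16 / 0.90 = 17.8, rounded up to 18). The documents give no figure for missing samples or marker shift. The missing fractions, shifts and cut-offs below are assumptions, shown as ranges.

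**Dilution of mean change.** Let a fraction f of changes be replaced by zero, unrelated to the true change, whose mean is D. The filled-in mean is (1 − f) × D.

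- f = 0.3, 0.5, 0.7 gives 0.7 D, 0.5 D, 0.3 D.
- With a 25% response rate and 50% of samples missing in non-responders only, f = 0.75 × 0.50 = 0.375. A true shift of 1 SD then becomes 0.625 SD; simulation gives 0.63 SD, against 1.00 SD from observed samples.

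This factor applies to tissue pairs, and to blood only where baseline is the only earlier value.

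**False association with PFS.** The simulation used 18 patients, exponential PFS and a marker change (SD 1) unrelated to PFS. Patients with an event before week 8 have no C3D1 sample. Change was split at 0.5 SD and tested by log-rank at a nominal 5%. Simulation error is about one percentage point.

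| True mean shift | 10% early events | 20% | 30% |
|---|---|---|---|
| 1 SD, carried forward | 16–17% | 28% | 39% |
| 0.5 SD, carried forward | 8–9% | 13% | 19–20% |
| 0, carried forward | 6% | 7% | 9% |
| Observed samples only | about 7–9% | about 7–9% | about 7–9% |

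The observed-only rate exceeds 5% because the log-rank approximation is liberal at this size, so 7–9% is the comparator. With this fixed cut, inflation needs a real shift: zeros then fall in the low group while most observed values fall in the high group. The result depends on the cut. A median split inflates even at zero shift (about 9–23%), and reaches about 11–44% at 1 SD.

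**False association with response.** A pooled t-test of change by response was run with 25% responders and 40–50% of samples missing in non-responders only. Carry-forward rejects in 8.8–11.0% of trials at zero shift, 10.7–14.1% at 0.5 SD, 13.1–19.8% at 1 SD and 16.9–25.6% at 1.5 SD. Observed samples give 4.4–5.8%. With 30% missing in both groups, carry-forward gives 4.3–5.0%. If gaps do not depend on outcome, there is no inflation.

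**Are early gaps plausible?** Median treatment duration in the anal-canal study cited in Protocol 1.6.2 was 85 days. If durations were exponential and carried over to this trial (both assumed), 1 − 2^(−56/85) = 37% would stop before day 56. That is a rough proxy, but it makes 10–30% look unexceptional.

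**HIV.** In the same study 9 of 94 patients were HIV-positive. If that share applied here, 18 × 9/94 = 1.7 patients are expected, with probability (85/94)^18 = 0.16 of none.

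**The case against.** The best reply is that the SAP never says that biomarkers are imputed. They have their own analysis set, built on evaluable samples, and a separate report; the analysis runs only if enough samples exist; and a paired comparison naturally means patients with both samples. SAP 5.1 also asks for observed data at each time point, SAP 6.2 requires outputs to show the number contributing, and exploratory p-values are descriptive.

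Much of this stands. Analysis of observed samples may well be what is intended. A reader might infer that the SAP deliberately imputes biomarkers and so biases the resistance analysis outright. The documents do not support that: the reach of the rule is read from a residual sentence and from the absence of an exemption.

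The safeguards still do not settle the matter. The Exploratory Set is defined per patient, so a patient with only a baseline sample can belong to it. Sample adequacy has no threshold and governs whether the analysis runs, not how gaps are filled. The sensitivity rows in SAP Tables 1 and 2 repeat the analysis on the per-protocol set, which does not test carry-forward.

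Two other strong readings also fail. One is that every missed viral load hides a loss of control. Viral load is measured every 8 weeks in the first year, with a final end-of-treatment sample, and a rebound already seen would itself be carried forward. The other is that all paired changes shrink by the missing fraction. For blood, an available C3D1 value is carried instead of baseline.

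**Conclusion.** The point holds conditionally and is minor. SAP 5.4.5 as written reaches follow-up biomarkers, CD4 count and viral load. If applied, it pulls mean change toward zero, in full proportion to the missing fraction for tissue pairs and wherever baseline is the only earlier value.

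False marker-outcome associations are possible but need outcome-related gaps and, with a fixed cut, a true on-treatment shift. A reader might take 17–39% as a general error rate. It belongs to one assumed setting (1 SD shift, 0.5 SD cut, 10–30% early events), falls to 8–19% at 0.5 SD and vanishes at zero shift. The documents specify neither such a test nor such a cut. The HIV part concerns the description of perhaps one or two patients.

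The primary ORR analysis is untouched because missing response counts as non-response.

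**What to change.** Add two or three sentences to SAP 5.4.5:

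- Carry-forward does not apply to biomarker, CD4 or viral-load data; only observed values are used, as already planned for maximum tumor shrinkage.
- C3D1 change analyses include only patients with a C3D1 sample, and the resistance analysis only patients with both samples.
- Tables give the number of samples or pairs and the reasons for missing ones.

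The cost is smaller numbers in the exploratory tables. If observed data were intended all along, the edit only puts that in writing. Showing viral load as detectable or undetectable at each visit would be a useful option but is not part of the required change.

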5.4.6 Subgroup Analysis

CBR, 6-month PFS, DoR, TTR, ORR, and OS according to RECIST v.1.1 together with ORR, CBR, and 6-month PFS according to irRECIST will be analyzed in patients' subgroups categorized based on baseline factors of potential prognostic value. The baseline factors will include but not limited to the following: (1) Prior treatments; (2) Number of previous regimens; (3) Type of previous regimens (e.g., platinum agents, radiotherapy); (4) Age; (5) Sites of metastases; (6) Race and geographic location (if applicable). We will utilize the Kaplan-Meier method and LogRank test. Multivariable Cox proportional hazards model for adjusting for multiple prognostic factors will be used to test the association between prognostic factors and the outcomes if sample size is adequate. Covariate estimates, HR and corresponding 95% CIs, applicable test statistics, and P-values will be presented. We will use the Breslow method for tie handling in survival analysis. P-values and 95% CIs for HR will be based on Wald test. The assumption of proportional hazards will be assessed by plotting the hazards over time.

For binary outcomes we will use chi-squared test for binary outcomes followed by multivariate logistic regression for adjusting for multiple prognostic factors. We will examine the residuals to assess model assumptions.

For all tests, we will use two-sided P-values with alpha=0.05 level of significance and P-values ≤ 0.05 will indicate statistical significance. The P-values emerging from these analyses will not be interpreted in a confirmative sense but will be considered of descriptive nature only. Analysis will be performed on the ITT and PP sets. ITT will be considered the primary population for the analysis.

Forest plots will be presented to describe all these analyses.

Table 3. Time-to-Event Estimands

Estimand	Population	Variable	Intercurrent event strategy	Summary measure
PFS subgroup analysis	FAS set	PFS	Multivariate Cox proportional hazards model adjusted for baseline prognostic factors. Breslow method for tie handling in survival analysis will be used. P-values and the 95% confidence intervals for hazard ratio will be based on Wald test.	Forest plot will report for each baseline prognostic subgroup: - number and % of patients - adjusted HR (95%CI) - interaction p-value - median survival time - 6-month survival rate (95%CI)
irPFS subgroups analysis	FAS set	irPFS	Same as above	Same as above
TTR subgroups analysis	FAS set	TTR	Same as above	Same as above
DoR subgroups analysis	FAS set	DoR	Same as above	Same as above
OS subgroups analysis	FAS set	OS	Same as above	Same as above

Table 4. Binary Outcomes Estimands

Estimand	Population	Variable	Intercurrent event strategy	Summary measure
ORR subgroup analysis	FAS set	ORR	Multivariate logistic regression model adjusted for baseline prognostic factors. P-values and the 95% confidence intervals for odds ratio will be based on Wald test.	Forest plot will report for each baseline prognostic subgroup: - % patients (95%IC) - adjusted OR (95%CI) - interaction p-value - proportion difference (95%CI)
CBR subgroup analysis	FAS set	CBR	Same as above	Same as above
irORR subgroup analysis	FAS set	irORR	Same as above	Same as above
irCBR subgroup analysis	FAS set	irCBR	Same as above	Same as above

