8.4.8 Subgroup Efficacy Analysis

CBR, 6-month PFS, DoR, TTP, ORR, and OS according to RECIST v.1.1 together with ORR, CBR, and 6-month PFS according to irRECIST will be analyzed in patients' subgroups categorized based on baseline factors of potential prognostic value. The baseline factors will include but not limited to the following: (1) Prior treatments; (2) Number of previous regimens; (3) Type of previous regimens (e.g., platinum agents, radiotherapy); (4) Age; (5) Sites of metastases; (6) Race and geographic location (if applicable). We will utilize the Kaplan-Meier method and LogRank test. Multivariable Cox proportional hazards model for adjusting for multiple prognostic factors will be used to test the association between prognostic factors and the outcomes if sample size is adequate. Covariate estimates, *hr* and corresponding 95% Cis, applicable test statistics, and P-values will be presented. We will use the Breslow method for tie handling in survival

analysis. P-values and 95% CIs for *hr* will be based on Wald test. The assumption of proportional hazards will be assessed by plotting the hazards over time.

For binary outcomes we will use chi-squared test for binary outcomes followed by multivariate logistic regression for adjusting for multiple prognostic factors. We will examine the residuals to assess model assumptions.

For all tests, we will use two-sided P-values with $\alpha \leq 0.05$ level of significance and P-values ≤ 0.05 will indicate statistical significance. The P-values emerging from these analyses will not be interpreted in a confirmative sense but will be considered of descriptive nature only. Analysis will be performed on the ITT and PP sets. ITT will be considered the primary population for the analysis.

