1.2 Type of Study

This is a multicenter, open-label, single-arm, phase II clinical trial to evaluate the efficacy and safety of the INCMGA00012 in progressive advanced PSqCC patients, previously treated or not with chemotherapy.

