1.6 Sample Size

A total of 18 patients will be enrolled and the defined primary endpoint is ORR.

Justification of Sample Size:

The sample size calculation is based on an exact binomial test. The clinical trial is designed to demonstrate an ORR of at least 25% and to exclude a rate of less than 5% ($p_0=0.05$, $p_1=0.25$, $\alpha =0.05$, $\beta=0.80$, A'herne's exact design). At least 3 responders (18.8%) among 16 evaluable patients will be adequate to justify the investigation of this strategy in further clinical trials. Considering a drop-out rate of 10%, a sample size of 18 patients will be needed to attain 80% power at nominal level of one-sided alpha of 0.05.

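### With about 4.5 expected responders, the unconditional multivariable logistic models for response and the adjusted Cox models for TTR and DoR will mostly have no finite fit if the six listed factors enter together, and the interaction p-value has no named term in a single arm

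*SAP*

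**What the plan says.** SAP 1.2 describes the trial: "This is a multicenter, open-label, single-arm, phase II clinical trial". SAP 1.6 gives the size: "A total of 18 patients will be enrolled and the defined primary endpoint is ORR".

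SAP 5.4.6 lists six baseline factors for subgroup analysis (prior treatments, number of previous regimens, type of previous regimens, age, sites of metastases, race and geography) and leaves the list open. Two kinds of model follow:

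- **Binary endpoints.** "For binary outcomes we will use chi-squared test for binary outcomes followed by multivariate logistic regression for adjusting for multiple prognostic factors". No condition on sample size is attached. Table 4 gives the same model for ORR, CBR, irORR and irCBR, "Multivariate logistic regression model adjusted for baseline prognostic factors", with Wald p-values and intervals. Protocol 8.4.8 also plans "multivariate logistic regression for adjusting for multiple prognostic factors".
- **Time-to-event endpoints.** The text makes the multivariable Cox model conditional on an adequate sample size but gives no threshold. Table 3 lists the adjusted Cox model for PFS, irPFS, TTR, DoR and OS without repeating the condition.

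Both tables also ask for an "interaction p-value" per subgroup, to be shown on forest plots. Table 4 already asks for the subgroup percentage and the difference in proportions, each with a 95% interval. The same section calls the subgroup p-values descriptive.

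**The concern.** A logistic model has a finite maximum likelihood estimate only if no combination of the covariates separates responders from non-responders. A Cox model has an equivalent requirement. With four or five responders, a few binary factors are often enough to break it. The software then stops at an arbitrary iteration and prints an extreme odds ratio or hazard ratio with a Wald interval that means nothing. TTR has the responders as its only events. DoR is computed in the responders only (SAP 5.4.1.1), so both inherit the problem.

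The interaction p-value is a separate defect. Treatment is constant in one arm, so a treatment-by-factor term cannot be estimated, and the SAP names no other variable for the factor to interact with.

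At stake are the subgroup forest plots. Some entries would depend on the software, and any fallback would be chosen after the data were seen.

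**Working it through.** **1. The plan's own figure.** Inputs from SAP 1.6: null rate 5%, target 25%, one-sided alpha 0.05, power 80%, 10% drop-out. Its rule is: "At least 3 responders (18.8%) among 16 evaluable patients will be adequate to justify".
- Alpha = P(X ≥ 3 | 16, 0.05) = 0.0429.
- Power = P(X ≥ 3 | 16, 0.25) = 0.803.
- Enrolment = 16 / 0.9 = 17.8, rounded up to 18.

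The design figure reproduces.

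**2. Responders available.** 18 × 0.25 = 4.5. With the 27.3% response rate that Protocol 8.2 cites from the vinflunine trial, 18 × 0.273 = 4.9. At 25%, P(3 or fewer) = 0.306 and P(4 or 5) = 0.717 − 0.306 = 0.411.

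**3. Chi-squared step.** The smallest expected cell is 9 × 4.5 / 18 = 2.25 for a 9/9 split and 6 × 4.5 / 18 = 1.5 for a 6/12 split, so the large-sample approximation is poor.

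**4. One-factor logistic, by hand.** The odds ratio is not finite if any cell of the 2×2 table is zero. At 25% response:
- 9/9 split: 1 − (1 − 0.75^9 − 0.25^9)² = 1 − 0.925² = 0.14.
- 6/12 split: 1 − (1 − 0.75^6 − 0.25^6)(1 − 0.75^12 − 0.25^12) = 1 − 0.822 × 0.968 = 0.20.

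Letting the split vary at random with prevalence 0.33 to 0.5 gives about 16–27%.

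**5. Several factors, by simulation.** Existence of the fit was checked by linear programming in 300–500 simulated data sets per setting (Monte Carlo error about 4–6 points). These assumptions are not in the documents: one binary term per factor, independent factors, no true effect, and the event fractions shown. For ORR at prevalence 0.33 to 0.5, no finite fit exists in about 40–54% of trials with three factors and 70–80% or more with six. Six-term results by endpoint, at prevalence 50% / 30%:

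| Endpoint and model | Assumed events or patients | No finite fit |
|---|---|---|
| ORR, logistic | 18 × 0.25 = 4.5 | 68% / 84% |
| CBR, logistic (45.5%, Protocol 8.2) | 18 × 0.455 = 8.2 | 41% / 65% |
| TTR, Cox | about 4.5 | 84% / 86% |
| DoR, Cox | 4 or 5 patients | 100% |
| PFS, OS, Cox, 60% events | 18 × 0.60 = 10.8 | 11% / 28% |
| PFS, OS, Cox, 85% events | 18 × 0.85 = 15.3 | 2% / 8% |

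irORR and irCBR were taken to behave like ORR and CBR, and irPFS like PFS. The DoR result needs no simulation: five patients give at most four independent covariate contrasts, fewer than six terms. Even one-factor DoR Cox fits fail in 45–69% of data sets of four or five patients.

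**6. Overfitting where the fit exists.** PFS and OS have 10.8 / 6 = 1.8 to 15.3 / 6 = 2.6 events per term.

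**7. Interaction.** Treatment-by-factor cannot be estimated because treatment does not vary. If all pairwise factor interactions were meant, the model would have 1 + 6 + 15 = 22 parameters for 18 patients.

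**The case against.** The best defence has five parts.

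- **The analyses are descriptive.** SAP 5.4 labels all efficacy analysis exploratory, and the primary test is untouched. This stands and limits the consequence. It does not make a missing estimate exist, and the same paragraph says p-values at or below 0.05 will indicate statistical significance.
- **Cox regression is not required outright.** A reader of Table 3 alone might infer that it is. The text of SAP 5.4.6 and Protocol 8.4.8 makes it conditional, so that reading fails. What remains is that the condition has no threshold and the table omits it.
- **Six simultaneous terms is one reading.** The text speaks of multiple factors and never says that all enter one model. This stands, so the result is given for one, three and six. With a single factor most ORR fits do exist.
- **Most models in the section might be thought to fail.** The numbers do not support that across all nine endpoints. PFS, irPFS and OS do not depend on the responder count and usually fit; CBR and irCBR are borderline.
- **Part of the remedy is already planned.** Table 4 includes subgroup proportions with intervals, and SAP 5.1 calls for exact intervals for binary endpoints. This stands; the fix keeps them.

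The interaction could be meant as factor-by-factor, since SAP 5.4.7 considers covariate-by-biomarker interactions. SAP 5.4.6 does not say so.

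**Conclusion.** The point holds for ORR and irORR logistic models, for TTR and DoR Cox models, and for the interaction p-value. With about 4.5 responders, the ORR logistic fit is missing in about 16–27% of trials with one factor, 40–54% with three and 70–80% or more with six. Six-term TTR fits are missing in about 85% and DoR fits essentially always. CBR and irCBR are borderline. PFS, irPFS and OS need a stated event threshold because of overfitting, not because the fits fail.

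The percentages rest on independent binary factors and assumed prevalences. Independence is lenient here: prior treatment, number of regimens and type of regimen overlap by construction, and factors with several levels add terms. The interaction point rests on no such assumption. The change should be made, but it does not touch the primary conclusion.

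**What to change.** In SAP 5.4.6 and Tables 3 and 4:

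1. For ORR, CBR, irORR and irCBR, keep the planned subgroup proportions, shown as responders/n with a Clopper-Pearson interval. Give the difference with an exact interval, and replace the chi-squared test with Fisher's exact test.
2. If an odds ratio is wanted, use one-factor exact or Firth logistic regression in place of the multivariable Wald model.
3. Delete the adjusted Cox models for DoR and TTR.
4. Delete every interaction p-value. Protocol 8.4.8 does not ask for one.
5. For PFS, irPFS and OS, carry the sample-size condition into Table 3 with a minimum event count fixed in advance.
6. List the departure from Protocol 8.4.8 in SAP 5.7, since the protocol also plans the chi-squared test and the logistic models.

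The cost is SAP wording and one entry in the list of changes, with less output and no new data. The downside is that there are no adjusted estimates for the response endpoints; if the full factor list were entered, most of those for ORR would not have existed.

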1.4 Study Design

A total of 18 patients with unresectable locally advanced or metastatic PSqCC will be enrolled into this trial.

INCMGA00012 should be administered intravenously, at flat dose of 500 mg over one hour (\pm 15 minutes) or 30 minutes (-5/+ 15 min) using a filter on day 1 of each 28-day cycle (every 4 weeks). Infusion rate may be reduced if an infusion reaction occurs.

In the absence of progression of disease or unacceptable toxicity, treatment with INCMGA00012 will continue based on physician criteria for up to 2 years.

Tumor assessments per RECIST v.1.1 and irRECIST will be performed approximately every 8 weeks (\pm 7 days) for the first 6 months and every 12 weeks (\pm 7 days) thereafter until PD, treatment discontinuation, the start of new anti-cancer treatment, withdrawal of consent, death, or the end of study (EoS), whichever occurs first. Tumor assessments will be performed on the specified schedule regardless of treatment delays.

The primary endpoint is ORR.

For estimation of ORR, CBR, DoR, PFS, and OS, tumor response will be based on RECIST v.1.1. In patients who continue treatment beyond radiographic PD per RECIST v.1.1, tumor response (ORR, CBR, and PFS) may continue to be assessed using irRECIST criteria until study treatment discontinuation.

Safety assessments will include the incidence, nature, and severity of AEs and laboratory abnormalities graded per the NCI-CTCAE v.5.0. Laboratory safety assessments will include the regular monitoring of hematology, blood chemistry, coagulation, and thyroid function testing.

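### The subgroup plan fixes a chi-squared test and Breslow ties for 18 men and attaches a significance label to p-values it calls descriptive: a minor fault of method, not touching the primary ORR test

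*SAP*

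**What the plan says.** SAP 5.4.6 covers nine outcomes (six by RECIST, three by irRECIST) across at least six baseline factors. The wording in protocol 8.4.8 is almost the same.

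- Binary outcomes: "For binary outcomes we will use chi-squared test for binary outcomes", followed by logistic regression. No exact alternative, expected-count condition or statement on continuity correction is given.
- Time-to-event outcomes: "We will use the Breslow method for tie handling in survival analysis". Table 3 repeats Breslow and Wald inference for PFS, irPFS, TTR, DoR and OS.
- Labelling: two-sided p-values at or below 0.05 "will indicate statistical significance". The next sentence says the p-values "will be considered of descriptive nature only".

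The size of the trial comes from SAP 1.6: "A total of 18 patients will be enrolled and the defined primary endpoint is ORR". Scan timing comes from SAP 1.4: "Tumor assessments will be performed on the specified schedule regardless of treatment delays". Scans are eight-weekly for six months and twelve-weekly afterwards, each with a ±7-day window.

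**The concern.** The chi-squared test relies on a large-sample approximation that needs adequate expected counts in every cell. With 4 or 5 responders among 18 men, no two-group ORR table comes near the usual minimum of 5. The p-value for a given table may then differ from the exact one by enough to cross 0.05.

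Breslow's approximation biases hazard ratios toward 1 when many events share a date. Progression and response are found at scheduled scans, so PFS, irPFS and TTR could have such ties.

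The labelling gives the report's author two instructions that pull apart: call a result significant at 0.05, and treat it as descriptive. What is at stake is how individual subgroup contrasts are reported, not whether the trial succeeds.

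**Working it through.** **The plan's own figure.** SAP 1.6 gives a null rate of 5%, a target of 25%, success at 3 or more responders of 16, 10% drop-out, and "80% power at nominal level of one-sided alpha of 0.05". With X binomial on 16 patients, P(X ≥ 3) is 0.0429 at 5% and 0.8029 at 25%. Then 16/0.9 = 17.8, rounded up to 18. The stated design reproduces.

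**Expected responders.** 18 × 0.25 = 4.5, so 4 or 5. In a subgroup of n₁ men with m responders in total, the expected responder count is m·n₁/18. Its largest value in the smaller group is 5 × 9/18 = 2.5.

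**Single tables.** For cells a, b, c, d, the uncorrected statistic is 18(ad − bc)² divided by the product of the four margins. Fisher's p sums the hypergeometric probabilities of tables no more likely than the one observed. With 4 responders the denominator is C(18,4) = 3060.

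- 4/9 against 0/9: 18·36²/(9·9·4·14) = 5.14, p = 0.023. Fisher: 2·126/3060 = 0.082.
- 3/6 against 1/12: 18·30²/(6·12·4·14) = 4.02, p = 0.045. Fisher: (240 + 15)/3060 = 0.083.
- 2/3 against 2/15: 18·24²/(3·15·4·14) = 4.11, p = 0.043. Fisher: (315 + 15)/3060 = 0.108.

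With Yates correction the same tables give 0.089, 0.161 and 0.205.

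**Chance-flag rate at p ≤ 0.05.** This is by full enumeration with no true subgroup difference, using the uncorrected chi-squared test.

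| Split | Expected responders, smaller group (4 / 5 responders) | Chi-squared, 4 responders | Fisher, 4 | Chi-squared, 5 responders | Fisher, 5 |
|---|---|---|---|---|---|
| 9/9 | 2.0 / 2.5 | 8.2% | 0% | 2.9% | 2.9% |
| 8/10 | 1.8 / 2.2 | 9.2% | 2.3% | 3.6% | 3.6% |
| 7/11 | 1.6 / 1.9 | 1.1% | 1.1% | 10.1% | 4.7% |
| 6/12 | 1.3 / 1.7 | 8.3% | 0.5% | 2.2% | 2.2% |
| 5/13 | 1.1 / 1.4 | 4.4% | 4.4% | 0.8% | 0.8% |
| 4/14 | 0.9 / 1.1 | 1.9% | 1.9% | 4.4% | 4.4% |
| 3/15 | 0.7 / 0.8 | 10.8% | 0.5% | 1.2% | 1.2% |

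Averaged over responder counts at a 25% response rate, the size across these splits is 3.3% to 5.8% for uncorrected chi-squared, 0.6% to 1.2% with Yates correction, and 1.2% to 3.0% for Fisher.

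**Ties.** Two groups of 9 men were simulated with exponential PFS observed on the scan calendar. The documents give no PFS median or subgroup hazard ratio, so the medians (12 and 26 weeks) and hazard ratios are assumptions. Entries are median estimated hazard ratios.

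| True HR, median PFS | Scans on nominal day: Breslow / Efron | Scans spread over ±7 days: Breslow / Efron |
|---|---|---|
| 2, 12 weeks | 1.67 / 1.97 | 1.99 / 2.02 |
| 2, 26 weeks | 1.86 / 2.04 | 2.00 / 2.02 |
| 3, 12 weeks | 2.06 / 2.75 | 2.74 / 2.83 |
| 3, 26 weeks | 2.49 / 3.01 | 3.09 / 3.11 |

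A separate run at a true hazard ratio of 2.5 gave 1.80 / 2.34 on nominal days and 2.41 / 2.47 with the spread. The spread-date loss in that run is (2.47 − 2.41)/2.47 = 2.4%. In the table it runs from 0.6% (3.09 against 3.11) to 3.2% (2.74 against 2.83).

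**The case against.** The strongest reply is that nothing decisive rests on these analyses. The SAP calls all efficacy analysis exploratory, accepts unadjusted testing in 5.1, and disclaims confirmatory use in 5.4.6. Averaged over responder counts, the chi-squared test is close to its nominal level, and a continuity-corrected version would under-flag. All of this stands, and it is why the point is minor. It does not rescue the choice of test: the p-value for the table actually observed can still mislead, and the plan leaves open two versions that disagree (0.023 or 0.089 for 4/9 against 0/9).

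Four stronger readings are tempting, and the documents do not support them.

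- A reader might infer that the ORR forest plot will mark chance splits as significant. Table 4 lists logistic odds ratios with Wald inference, interaction p-values and proportion differences, and no chi-squared p-value. Unadjusted Wald tests give 0.070 for 3/6 against 1/12 and 0.075 for 2/3 against 2/15; 4/9 against 0/9 is separated and yields no significant Wald result.
- A reader might infer that PFS hazard ratios will be markedly understated. SAP 5.4.1.1 dates radiological progression by the actual assessment, and deaths and clinical progression fall off the scan calendar. The text also makes the Cox model conditional on an adequate sample, though Table 3 does not repeat that.
- A reader might infer that Breslow adds false positives. It makes them rarer: with no true difference, a 12-week median and nominal scan days, rejection was 1.3% with Breslow and 4.0% with Efron.
- A reader might multiply 9 outcomes by 6 factors to get 54 looks, 54 × 0.05 = 2.7 expected flags, and 1 − 0.95⁵⁴ = 94% for at least one. The 94% needs independence, which RECIST and irRECIST versions of the same outcome do not have. Multiplicity is also openly declared, and changing the test or the tie method does not cure it.

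**Conclusion.** The point holds as a minor fault of method. For the simple binary subgroup comparisons, an uncorrected chi-squared test is unreliable table by table: its chance-flag rate ranges from about 1% to 11% by split with 4 responders, while averaging about 3% to 6% at a 25% response rate. This assumes two-group splits, 4 to 5 responders and no continuity correction. The error is erratic rather than uniformly inflated.

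Breslow is a small issue in practice. The loss is about 2% if scan dates spread over the permitted window and large only if they cluster on nominal days. It concerns PFS, irPFS and TTR; OS events are deaths and do not follow the scan calendar. These magnitudes rest on assumed medians and hazard ratios.

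The significance label conflicts in tone with the descriptive status that follows it. The primary ORR test, its decision rule and the sample size are untouched.

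**What to change.** In SAP 5.4.6 and Table 3:

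1. Name Fisher's exact test for binary subgroup comparisons. A mid-p version is not a substitute here, since it still flags two of the three example tables (0.041 for 4/9 against 0/9 and 0.044 for 3/6 against 1/12).
2. Replace Breslow with Efron or exact tie handling.
3. Delete the sentence part that makes p-values at or below 0.05 a mark of significance, and keep the descriptive statement.
4. Record the departure from protocol 8.4.8, which prescribes the same methods and label, in SAP 5.7.

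The cost is a few lines of SAP text and two SAS options. Fisher is conservative, with a size of about 1% to 3% here, which is acceptable for descriptive results. Efron has no drawback in this setting.
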